4.1.2. Part 1 Expansion

Part 1 expansion is a Phase 2 with an initial safety run-in that will employ a randomized, open-label, parallel-cohort design with the primary objective to assess the safety and preliminary efficacy of itacitinib in combination with corticosteroids compared with corticosteroids monotherapy and identify the appropriate dosing/schedule of itacitinib in combination with corticosteroids as initial treatment for cGVHD for Part 2. A total of up to 140 participants (35 per treatment group) with moderate or severe cGVHD will be randomized 1:1 to 1 of 4 treatment groups (Table 8), specifically: itacitinib 300 mg QD plus corticosteroids (Treatment Group A), itacitinib 400 mg QD plus corticosteroids (Treatment Group B), itacitinib 300 mg BID plus corticosteroids (Treatment Group C) or corticosteroids monotherapy (Treatment Group D).

Table 8: Treatment Groups and Dose Levels and Schedules

Treatment Group	Dose Level and Schedule
A	Itacitinib 300 mg QD plus corticosteroids
В	Itacitinib 400 mg QD plus corticosteroids
С	Itacitinib 300 mg BID plus corticosteroids; may be decreased to 200 mg BID if a boundary is reached during safety run. This treatment group was discontinued due to concern of a potential increase in relapse rate. Participants in this treatment group who were ongoing were allowed to reduce to 400 mg QD plus corticosteroids.
D	Corticosteroids monotherapy.

Randomization will be stratified by cGVHD risk status (moderate vs severe). Treatment groups B and C will have an initial safety run-in of 10 participants to determine safety and tolerability of the dose before expanding (see definition of DLT in Section 6.1.1.3). Participants enrolled in the safety run-in will be monitored continuously using the Bayesian approach (Section 10.4.1.1). Treatment Group C was discontinued as of Amendment 8 and participants in that treatment group who were ongoing were allowed to reduce to 400 mg QD plus corticosteroids.

Itacitinib treatment will continue until treatment failure (cGVHD progression, death, or initiation of new systemic cGVHD therapy), unacceptable toxicity, or withdrawal of consent. Participants will remain on study for a total of 37 months, including study treatment (up to 36 months), safety follow-up (30 days after EOT), and post-treatment GVHD follow-up (up to 24 months from Day 1), unless death or withdrawal of consent occurs earlier.

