10.4.1. Primary Analysis

10.4.1.1. Part 1 and Safety Run-In for Part 1 Expansion

The toxicity of itacitinib will be monitored continuously for each treatment group using the Bayesian approach of Thall et al (1995, 1996) as extended by Thall and Sung (1998). Dose-limiting toxicities are defined in Section 6.1.1.3.

Historical data on similar patients show a toxicity rate of 25%. The probability of toxicity for the historical data is modeled by beta distribution (Beta [25, 75]). The prior probability of toxicity for the experimental regimen is also modeled by beta distributions (Beta [0.5, 1.5]), which have the same means as the corresponding beta distributions for the historical data. Denoting the historical probability of toxicity rate by p(TOX,H), the following decision criteria will be applied:

Stop if Prob
$$\{p(TOX,H) + \delta TOX < p(TOX,E) | data \} > 0.95$$
, where $\delta TOX = 0$

Participants from each treatment group will be monitored according to the following nonbinding stopping boundaries for toxicity in Table 25. If a boundary is reached, the sponsor and external DMC will investigate and decide on the most appropriate action.

Table 25: Toxicity Stopping Boundaries

# Participants (Inclusive)	Number of DLTs Required to Stop (Inclusive)
1-2	No limit
3-4	3
5-6	4
7-9	5
10-11	6
12-14	7
15-17	8
18-19	9
20	9

10.4.1.2. Part 2

The primary endpoint is Month 6 response rate, defined as the proportion of participants demonstrating a CR or PR at Month 6 as per standard criteria (Lee et al 2015). The comparison of Month 6 response rate between treatment cohorts will be conducted once the last participant completes the Month 6 visit or withdraws from the study. A CMH test with normal approximation will be used. Summary statistics and 95% CI will be provided.

Participants who have missing data for the Month 6 response rate assessment will be considered as nonresponders.

For the interim analysis, the statistical assumptions are specified in Section 10.5.

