9.2.2. Dose-Limiting Toxicities

Evaluation of DLTs was performed in Part 1 and in Part I expansion for the safety run-in population (first 10 participants) enrolled in Treatment Groups B and C. The toxicity of itacitinib will be monitored continuously for each treatment group using the Bayesian approach of Thall et al (1995, 1996) as extended by Thall and Sung (1998). Dose-limiting toxicities are defined in [Table 5](#). The DLTs will be summarized on the first 28 days of study treatment.

Table 5: Definitions of Dose-Limiting Toxicity

| Toxicity | Definition |
|----------------|--|
| Nonhematologic | 
Any \geq Grade 3 nonhematologic toxicity that can be reasonably attributed to study treatment. \geq Grade 3 nonhematologic toxicities that may be related to underlying GVHD (eg, nausea, vomiting, diarrhea, rash, dry eye) will not be considered as DLTs.Any \geq Grade 3 clinical chemistry laboratory abnormalities that are considered clinically significant and related to study treatment. Transient abnormal laboratory values without associated clinically significant signs and symptoms, manageable with adequate medical care, and not leading to hospitalization will not be considered as DLTs. |
| Hematologic | 
Grade 4 neutropenia lasting more than 7 days or a \geq 90% decrease in absolute neutrophil count from baseline that can reasonably be attributed to study treatment.Platelet count $< 10 \times 10^9/L$ related to study treatment that does not recover to at least $20 \times 10^9/L$ after 2 weeks with no requirement for platelet transfusion in the preceding 3 days. |

Historical data on similar patients show a toxicity rate of 25%. The probability of toxicity for the historical data is modeled by beta distribution (Beta [25, 75]). The prior probability of toxicity for the experimental regimen is also modeled by beta distributions (Beta [0.5, 1.5]), which have the same means as the corresponding beta distributions for the historical data. Denoting the historical probability of toxicity rate by $p(\text{TOX},\text{H})$, the following decision criteria will be applied:

Stop if $\text{Prob}\{p(\text{TOX},\text{H}) + \delta\text{TOX} < p(\text{TOX},\text{E}) | \text{data}\} > 0.95$, where $\delta\text{TOX} = 0$

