Participants from each treatment group will be monitored according to the following nonbinding stopping boundaries for toxicity in [Table 6](#). If a boundary is reached, the sponsor and external DMC will investigate and decide on the most appropriate action.

Table 6: Toxicity Stopping Boundaries

| # Participants (Inclusive) | Maximum Allowable Number of Toxicities (Inclusive) |
|----------------------------|---|
| 1-2 | No limit |
| 3-4 | 3 |
| 5-6 | 4 |
| 7-9 | 5 |
| 10-11 | 6 |
| 12-14 | 7 |
| 15-17 | 8 |
| 18-19 | 9 |
| 20 | 9 |

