9.2.3. Adverse Event Summaries

An overall summary of AEs by treatment group will include the following:

- Number (%) of participants reporting any TEAEs
- Number (%) of participants reporting any serious TEAEs
- Number (%) of participants reporting any Grade 3 and higher TEAEs
- Number (%) of participants reporting any DLTs
- Number (%) of participants reporting any TEAEs related to itacitinib
- Number (%) of participants who temporarily interrupted itacitinib because of TEAEs
- Number (%) of participants with itacitinib dose reductions because of TEAEs
- Number (%) of participants who permanently discontinued itacitinib because of TEAEs
- Number (%) of participants reporting any TEAEs related to corticosteroid
- Number (%) of participants who temporarily interrupted corticosteroid because of TEAEs
- Number (%) of participants with corticosteroid dose reductions because of TEAEs
- Number (%) of participants who permanently discontinued corticosteroid because of TEAEs
- Number (%) of participants who had a fatal TEAE

The following summaries will be produced by MedDRA term (if 10 or fewer participants appear in a table, a listing may be appropriate):

- Number (%) of participants reporting TEAEs by SOC and PT
- Number (%) of participants reporting TEAEs by PT in decreasing order of frequency
- Number (%) of participants reporting TEAEs by SOC, PT, and maximum severity

- Number (%) of participants reporting itacitinib treatment-related TEAEs by SOC and PT
- Number (%) of participants reporting itacitinib treatment-related TEAEs by PT in decreasing order of frequency
- Number (%) of participants reporting itacitinib treatment-related, Grade 3 or higher TEAEs by SOC and PT
- Number (%) of participants reporting any Grade 3 or higher TEAEs by SOC and PT
- Number (%) of participants reporting any Grade 3 or higher TEAEs by SOC and PT in decreasing order of frequency
- Number (%) of participants reporting serious TEAEs by SOC and PT
- Number (%) of participants reporting serious TEAEs by SOC and PT in decreasing order of frequency
- Number (%) of participants reporting itacitinib treatment-related, serious TEAEs by SOC and PT
- Number (%) of participants reporting TEAEs leading to itacitinib dose interruption by SOC and PT
- Number (%) of participants reporting TEAEs leading to itacitinib dose reduction by SOC and PT
- Number (%) of participants reporting TEAEs leading to discontinuation of itacitinib by SOC and PT

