11. CHANGES AND MODIFICATIONS TO THE ANALYSIS PLAN

All versions of the SAP are listed in [Table 8](#).

Table 8: Statistical Analysis Plan Versions

| SAP Version | Date |
|-------------|-------------|
| Original | 06 NOV 2019 |
| Amendment 1 | 03 MAR 2022 |

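### The SAP labels the DLT boundary counts as the most that may be tolerated, while the protocol labels the same counts as the trigger; the shared formula supports the protocol, so the SAP heading is one DLT too high

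*SAP*

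**What the plan says.** Protocol 10.4.1.1 and SAP 9.2.2 describe the same continuous monitoring rule for DLTs. The historical toxicity probability has a Beta(25, 75) distribution. For the new regimen, the SAP says: "The prior probability of toxicity for the experimental regimen is also modeled by beta distributions (Beta [0.5, 1.5"]). Both documents call for a stop when the posterior probability that the experimental toxicity rate exceeds the historical one is above 0.95, with a margin of zero.

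Each document then tabulates the rule. The counts and participant ranges are identical, but the column headings are not:

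- Protocol Table 25: "Number of DLTs Required to Stop (Inclusive"
- SAP Table 6: "Maximum Allowable Number of Toxicities (Inclusive"

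Both call the boundaries nonbinding. The SAP's sentence above its table reads: "If a boundary is reached, the sponsor and external DMC will investigate and decide on the most appropriate action". In the Part 1 expansion the rule applies to Groups B and C, each with an "initial safety run-in of 10 participants to determine safety and tolerability of the dose before expanding" (protocol 4.1.2). Sections 11.1 and 11.2 of the SAP do not list any change to the boundary.

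**The concern.** The two headings cannot both describe the same column. A number required to stop is the smallest count that triggers action. A maximum allowable number, inclusive, is the largest count that does not. With the same figures beneath them, the two rules differ by one DLT in every row that carries a count.

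At stake is the accuracy of a stated safety threshold. Anyone applying or reporting the SAP table literally would treat 6 DLTs in 10 as acceptable when the protocol treats that result as reaching the boundary. Reaching it matters beyond the DMC review, because protocol Table 8 and SAP Table 2 also link it to a possible dose decrease in Group C. A clinical study report that copied the SAP heading would disagree with the protocol.

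**Working it through.** **Inputs** (the same in protocol 10.4.1.1 and SAP 9.2.2)

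- Historical toxicity probability: p_H ~ Beta(25, 75), mean 0.25.
- Prior for the experimental regimen: p_E ~ Beta(0.5, 1.5), mean 0.25.
- Margin 0; stop if the posterior probability exceeds 0.95.
- Run-in size: 10 per group.

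**Formula.** After x DLTs in n participants, p_E ~ Beta(0.5 + x, 1.5 + n − x). The monitored quantity is

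P(p_E > p_H | x, n) = ∫ f_H(h) · [1 − F_E(h)] dh,

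where f_H is the Beta(25, 75) density and F_E is the distribution function of the updated p_E. It was evaluated by numerical integration for n = 1 to 20.

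**Worked case, n = 10.**

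- x = 5: p_E ~ Beta(5.5, 6.5), posterior 0.925, no stop.
- x = 6: p_E ~ Beta(6.5, 5.5), posterior 0.978, stop.
- x = 7: p_E ~ Beta(7.5, 4.5), posterior 0.995, stop.

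The smallest stopping count is 6, which is the tabulated figure.

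**Reproducing the whole table**

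| Participants | Tabulated count | Smallest x with posterior > 0.95 | Posterior at that x, for each n in turn |
|---|---|---|---|
| 1–2 | no limit | none (2 of 2 gives 0.940) | – |
| 3–4 | 3 | 3 | 0.982, 0.952 |
| 5–6 | 4 | 4 | 0.983, 0.963 |
| 7–9 | 5 | 5 | 0.985, 0.971, 0.951 |
| 10–11 | 6 | 6 | 0.978, 0.963 |
| 12–14 | 7 | 7 | 0.983, 0.972, 0.957 |
| 15–17 | 8 | 8 | 0.978, 0.967, 0.953 |
| 18–19 | 9 | 9 | 0.974, 0.964 |
| 20 | 9 | 9 | 0.9502 |

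With one DLT fewer the posterior stays below 0.95 at every n from 3 to 20; it ranges from 0.787 (n = 4) to 0.944 (n = 12). The tabulated count is therefore the trigger throughout, and the largest count that does not trigger is one less.

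As a check on the source of the table, fixing p_H at 0.25 instead of giving it the Beta(25, 75) distribution changes the trigger to 6, 7 and 8 at n = 12, 15 and 18. The table shows 7, 8 and 9 there, so it follows the rule as written. That variant gives lower triggers, so it does not support the SAP heading either.

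**What the heading changes.** Take the trigger as the listed count (protocol heading) or the listed count plus one (SAP heading).

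*One look at n = 10, true rate 25%.*

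- P(X ≥ 6) = 0.01622 + 0.00309 + 0.00039 + 0.00003 + 0.000001 = 0.0197.
- P(X ≥ 7) drops the first term, leaving 0.0035.

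*A look after every participant up to 10*, by exact recursion, assuming each outcome is known before the next look:

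| True DLT rate | Protocol heading | SAP heading |
|---|---|---|
| 10% (assumed) | 0.46% | 0.02% |
| 25% (documents' rate) | 8.5% | 1.4% |
| 40% (assumed) | 33.2% | 11.3% |
| 60% (assumed) | 77.3% | 50.2% |

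Under the SAP heading 3 DLTs in 3 participants could never cross, although the formula gives 0.982 there and the table reserves its no-limit entry for n = 1–2.

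**The case against.** The strongest reply is that the SAP's own context shows what is meant. The table is titled as stopping boundaries, the sentence above it acts once a boundary is reached, and the formula comes just before. Read literally, the heading leaves n = 3 with no effective limit, which a careful reader would see is unintended. On this view the heading is loose wording and no calculation is wrong.

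Much of that stands. The counts are correct, and this is a labelling error. But those features show that the SAP contradicts its own heading; they do not repair it. The word inclusive, attached to a maximum, permits the listed number outright.

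The second reply is that nothing turns on it, and here the evidence is substantial.

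- The boundaries are nonbinding.
- SAP Amendment 1, dated 03 MAR 2022, puts the work in the past: "Evaluation of DLTs was performed in Part 1 and in Part I expansion for the safety run-in population (first 10 participants").
- Part 1 had one investigator-assessed DLT in each cohort, with 10 per cohort past Day 28 (protocol 2.3.2.1).
- Groups B and C had enrolled 25 and 24 by 09 JUL 2021 (protocol 2.3.2.3), well beyond the run-in of 10.
- Group C was later closed over malignancy relapse (protocol 2.4).

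The run-in DLT counts for B and C are not given, but nothing suggests that either group was near 6 in 10.

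Two limits on the figures are also fair. With a 28-day DLT window, a look after every completed outcome is an idealisation; the single-look contrast is the plainer one. The 10% row is only an assumption: it echoes one DLT per 10 in Part 1, at other doses and without stated DLT-evaluable denominators.

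**Conclusion.** The concern holds and is minor. The SAP heading overstates the boundary by one DLT in every row with a count, judged against the formula the SAP itself states and against protocol Table 25. This conclusion rests only on the priors, margin and 0.95 cutoff printed in both documents.

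At the 25% rate the heading changes the chance of reaching the boundary by participant 10 from 2.0% to 0.35% with one look, or from 8.5% to 1.4% with a look after each participant. These figures assume independent outcomes with a common rate. They describe how the two readings behave and do not show that monitoring went wrong. No view is taken on whether the threshold is clinically suitable; the point is that the two tables and the shared formula must agree.

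**What to change.** Reconcile the heading of SAP Table 6 with the formula in SAP 9.2.2 and with protocol Table 25 by adopting the protocol's heading, "Number of DLTs Required to Stop (Inclusive"), and leave the counts unchanged. Keeping the SAP heading would instead mean lowering every count by one (2, 3, 4, 5, 6, 7, 8 and 8 for the rows from 3–4 to 20), which makes the two tables harder to compare.

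It would also help to state in the report which reading was applied in the Group B and C run-ins. SAP 9.2.3 already plans "Number (%) of participants reporting any DLTs" by treatment group. That row is not specific to the run-in participants, so the sentence should say which participants it covers.

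The cost is one column heading and, if wanted, one sentence. No new data or analysis is needed.

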9.2.3. Adverse Event Summaries

An overall summary of AEs by treatment group will include the following:

- Number (%) of participants reporting any TEAEs
- Number (%) of participants reporting any serious TEAEs
- Number (%) of participants reporting any Grade 3 and higher TEAEs
- Number (%) of participants reporting any DLTs
- Number (%) of participants reporting any TEAEs related to itacitinib
- Number (%) of participants who temporarily interrupted itacitinib because of TEAEs
- Number (%) of participants with itacitinib dose reductions because of TEAEs
- Number (%) of participants who permanently discontinued itacitinib because of TEAEs
- Number (%) of participants reporting any TEAEs related to corticosteroid
- Number (%) of participants who temporarily interrupted corticosteroid because of TEAEs
- Number (%) of participants with corticosteroid dose reductions because of TEAEs
- Number (%) of participants who permanently discontinued corticosteroid because of TEAEs
- Number (%) of participants who had a fatal TEAE

The following summaries will be produced by MedDRA term (if 10 or fewer participants appear in a table, a listing may be appropriate):

- Number (%) of participants reporting TEAEs by SOC and PT
- Number (%) of participants reporting TEAEs by PT in decreasing order of frequency
- Number (%) of participants reporting TEAEs by SOC, PT, and maximum severity

- Number (%) of participants reporting itacitinib treatment-related TEAEs by SOC and PT
- Number (%) of participants reporting itacitinib treatment-related TEAEs by PT in decreasing order of frequency
- Number (%) of participants reporting itacitinib treatment-related, Grade 3 or higher TEAEs by SOC and PT
- Number (%) of participants reporting any Grade 3 or higher TEAEs by SOC and PT
- Number (%) of participants reporting any Grade 3 or higher TEAEs by SOC and PT in decreasing order of frequency
- Number (%) of participants reporting serious TEAEs by SOC and PT
- Number (%) of participants reporting serious TEAEs by SOC and PT in decreasing order of frequency
- Number (%) of participants reporting itacitinib treatment-related, serious TEAEs by SOC and PT
- Number (%) of participants reporting TEAEs leading to itacitinib dose interruption by SOC and PT
- Number (%) of participants reporting TEAEs leading to itacitinib dose reduction by SOC and PT
- Number (%) of participants reporting TEAEs leading to discontinuation of itacitinib by SOC and PT
- Number (%) of participants reporting corticosteroid treatment-related TEAEs by SOC and PT
- Number (%) of participants reporting corticosteroid treatment-related TEAEs by PT in decreasing order of frequency
- Number (%) of participants reporting corticosteroid treatment-related, Grade 3 or higher TEAEs by SOC and PT
- Number (%) of participants reporting corticosteroid treatment-related, serious TEAEs by SOC and PT
- Number (%) of participants reporting TEAEs leading to corticosteroid dose interruption by SOC and PT
- Number (%) of participants reporting TEAEs leading to corticosteroid dose reduction by SOC and PT
- Number (%) of participants reporting TEAEs leading to discontinuation of corticosteroids by SOC and PT
- Number (%) of participants reporting fatal TEAEs by SOC and PT

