5.3. Analysis Populations

The populations that will be included in study-related analyses are described in [Table 4](#).

Table 4: Populations for Analysis

| Population | Description |
|---------------|---|
| ITT | All randomized participants |
| Safety | All enrolled/randomized participants who received at least 1 dose of study drug and/or reference therapy. Treatment groups for this population will be determined according to the actual treatment the participant received regardless of assigned study drug treatment. |
| Safety run-in | All participants enrolled in the safety run-in portion of the study who received at least 1 dose of study drug and/or reference therapy. Treatment groups for this population will be determined according to the treatment assignment on Day 1 regardless of the actual study drug the participant might take during their continued participation in the study. |
| PK evaluable | All participants who received at least 1 dose of study drug and/or reference therapy and provided at least 1 postdose plasma sample (1 PK measurement). The study pharmacokineticist will review data listings of study drug administration and sample records to identify participants to be excluded from analyses of PK data. |

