9.1. General Considerations

All safety analyses will be conducted for the safety population and summarized by treatment group. Summary tables may be replaced with listings when appropriate. For instance, an AE frequency table may be replaced with a listing if it only contains a few unique PTs reported on relatively few participants.

In order to accommodate the changes proposed in Protocol Amendment 8 that resulted in discontinuation of Treatment Group C (300 mg BID) and subsequent dose reduction of ongoing participants in Treatment Group C to 400 mg QD, safety tables (specifically AEs) will be presented for the 300 mg BID group with participants who are subject to dose reduction and censored at the date of switching to the lower dose (400 mg QD). An overall summary including both dose groups (participants included before and after the dose reduction) will also be presented.

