| 2.2.1 | Summary of Overall Response Rate at Months 3, 6, and 12 | Safety |
| 2.2.2 | Summary of Nonrelapse Mortality Rate | Safety |
| 2.2.3 | Summary of Duration of Response | Safety |
| 2.2.4 | Summary of Time to Response | Safety |
| 2.2.5 | Summary of Relapse Rate of Malignant and Nonmalignant Hematologic Diseases | Safety |
| 2.2.6 | Summary of Time to Primary Hematologic Disease Relapse | Safety |
| 2.2.7 | Summary of Overall Survival | Safety |
| 2.2.8 | Summary of Best Overall Response | Safety |
| 2.2.8.1 | Summary of Best Overall Response by GVHD Organ Involved | Safety |

| Table No. | Title | Population |
|-----------|---|------------|
| 2.2.8.2 | Summary of Best Overall Response for Skin Sclerotic Findings Subgroup | Safety |
| 2.2.9 | Summary of Failure-Free Survival | Safety |
| 2.2.11 | Summary of Number of Participants With $\geq 50\%$ Reduction in Daily Corticosteroid Dose at Day 180 | Safety |
| 2.2.12 | Summary of Participants Successfully Tapered Off All Corticosteroids at Day 180 | Safety |
| 2.2.13 | Summary of Number of Participants With $\geq 50\%$ Reduction in Daily Corticosteroid Dose by (4-Week) Time Interval Up to Month 6 | Safety |
| 2.2.14 | Summary of Participants Successfully Tapered Off All Corticosteroids by (4-Week) Time Interval Up to Month 6 | Safety |
| 3.1.1 | Summary of Itacitinib Exposure, Duration of Exposure, and Dose Adjustment | Safety |
| 3.1.2 | Summary of Itacitinib Compliance | Safety |
| 3.1.3 | Summary of Corticosteroid Exposure, Duration of Exposure, and Dose Adjustment | Safety |
| 3.2.1 | Overall Summary of Treatment-Emergent Adverse Events | Safety |
| 3.2.2 | Summary of Treatment-Emergent Adverse Events by MedDRA System Organ Class and Preferred Term | Safety |
| 3.2.3 | Summary of Treatment-Emergent Adverse Events by MedDRA Preferred Term in Decreasing Order of Frequency | Safety |
| 3.2.4 | Summary of Treatment-Emergent Adverse Events by MedDRA System Organ Class, Preferred Term, and Maximum Severity | Safety |
| 3.2.5 | Summary of Itacitinib Treatment-Related, Treatment-Emergent Adverse Events by MedDRA System Organ Class and Preferred Term | Safety |
| 3.2.6 | Summary of Itacitinib Treatment-Related, Treatment-Emergent Adverse Events by MedDRA Preferred Term in Decreasing Order of Frequency | Safety |
| 3.2.7 | Summary of Itacitinib Treatment-Related, Grade 3 or Higher Treatment-Emergent Adverse Events by MedDRA System Organ Class, and Preferred Term | Safety |

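### The by-group DLT percentage is placed on the safety population although only Part 1 and the first 10 participants of Groups B and C were evaluated, so it is understated by up to 3.5-fold and unassessed participants appear DLT-free

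*SAP*

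**What the plan says.** SAP 9.2.3 lists the contents of the overall adverse event summary by treatment group. One line is "Number (%) of participants reporting any DLTs", with no denominator of its own.

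The population comes from two other places. SAP 9.1 states: "All safety analyses will be conducted for the safety population and summarized by treatment group". Appendix A gives Table 3.2.1 as "Overall Summary of Treatment-Emergent Adverse Events | Safety".

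SAP 9.2.2 says who was evaluated for DLTs: Part 1 and, in the expansion, an evaluation "for the safety run-in population (first 10 participants) enrolled in Treatment Groups B and C". It adds a time window: "The DLTs will be summarized on the first 28 days of study treatment". It names no denominator for that summary.

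SAP 5.3 defines a safety run-in population ("All participants enrolled in the safety run-in portion of the study who received at least 1 dose of study drug and/or reference therapy"), but Appendix A assigns no table to it. Protocol 6.1.1.3 has an evaluability rule (at least 21 of 28 doses at the assigned level, or a DLT). The SAP does not turn that rule into an analysis population.

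**The concern.** The numerator and the denominator of the DLT percentage come from different sets of people. In Group B, DLTs can be counted among about 10 assessed participants, while the planned denominator is 35. In Group D nobody was assessed, so a printed zero would mean that no one looked, yet it would read as no toxicity. The same holds for Group A participants randomized in the expansion.

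This matters because DLT data through Day 28 are the primary endpoint of Part 1, and SAP 7.2 bases dose selection in the expansion primarily on the incidence and severity of adverse events across cohorts. A by-group DLT row with unequal ascertainment invites a comparison between columns that the data cannot support.

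**Working it through.** **Inputs**
- Planned group size: 35, with 4 groups and 140 in total (SAP 3.1.2; 4 × 35 = 140). Protocol Table 3 counts qualifying Part 1 participants within the 35.
- Enrolment at the 09 JUL 2021 cutoff: A 32, B 25, C 24, D 26 (Protocol 2.3.2.3). Group C was discontinued as of Amendment 8 (30 SEP 2021).
- Part 1: 11 enrolled at 200 mg and 10 at 300 mg, 10 in each with 28 days completed, and one DLT in each cohort (Protocol 2.3.2.1).
- Assessed for DLTs: Part 1, and 10 each in Groups B and C (SAP 9.2.2).
- Historical toxicity rate 25%, modelled as Beta(25, 75); experimental prior Beta(0.5, 1.5); stop if the posterior probability exceeds 0.95 (SAP 9.2.2).

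**The plan's own figure.** The boundary at n participants is the smallest x with P(pE > pH) > 0.95, where pE ~ Beta(0.5 + x, 1.5 + n − x) and pH ~ Beta(25, 75). At n = 10, x = 5 gives 0.925 and x = 6 gives 0.978, so the boundary is 6, as tabulated. All entries for n = 1 to 20 reproduce when read as counts that trigger stopping, which is the heading in Protocol Table 25. The rule needs only run-in counts and run-in numbers.

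**Understatement factor.** With d DLTs among m assessed participants and N in the safety population, the table prints d/N where the rate among those assessed is d/m. The factor is N/m.

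| Column | N | m | N/m |
|---|---|---|---|
| Group B, planned size | 35 | 10 | 3.5 |
| Group B, July 2021 | 25 | 10 | 2.5 |
| Group C, July 2021 | 24 | 10 | 2.4 |
| Group A pooled with Part 1 300 mg, planned size | 35 | 10 | 3.5 |
| Group A, July 2021, if the 32 include Part 1 300 mg | 32 | 10 | 3.2 |
| Part 1 200 mg | 10 or 11 | 10 | 1.0 to 1.1 |
| Group A, newly randomized only | – | 0 | undefined |
| Group D | up to 35 | 0 | undefined |

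**What would be printed**
- 6 DLTs in a run-in of 10 (60%) would print as 6/35 = 17.1% at planned size. At the July 2021 sizes it would print as 6/25 = 24.0% in Group B or 6/24 = 25.0% in Group C.
- 3 in 10 (30%) would print as 3/35 = 8.6%.
- The one Part 1 DLT at 300 mg (1/10 = 10.0%) would print as 1/35 = 2.9% if those participants are pooled into Group A.

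The 6-of-10 and 3-of-10 cases are illustrations; the documents give no DLT counts for the expansion.

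**Is it corrected elsewhere?** Appendix A contains no DLT table. Its five listings cover enrolment and disposition, posttherapy medications, deaths, adverse events leading to itacitinib changes, and protocol deviations. None is for DLTs.

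**The case against.** The strongest reply is that the denominator is inferred. The DLT line states none, and the section specific to DLTs restricts evaluation to the run-in, so it could be taken to govern. The Safety label in Appendix A is also weak evidence: it is attached to every table, including baseline and exposure tables that SAP section 6 describes on the run-in population. This has some force, but SAP 9.2.2 supplies only a 28-day window. The sole stated population rule is the general one in SAP 9.1, and no planned table uses the run-in population. A programmer following the text would divide by the safety population.

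Other objections stand and limit the point:
- The stopping rule uses counts during the run-in, and reaching a boundary prompts sponsor and DMC review whatever this table later prints. A reader might infer from 17.1% against 25% that a toxic dose could pass unnoticed. The documents do not support that.
- A reader might infer that the row makes the itacitinib doses look safe for dose selection. The same overview reports Grade 3 or higher, serious and fatal events, and events leading to interruption, reduction or discontinuation, and the DMC reviews all safety data. The DLT count is also printed beside the percentage.
- Setting 2.9% at 300 mg beside 9.1% (1/11) at 200 mg requires a table that pools Part 1 300 mg into Group A and shows Part 1 200 mg alongside. Appendix A does not say whether Table 3.2.1 does this.
- The original SAP of 06 NOV 2019, which covered Part 1, is not among the documents. That no other DLT display is planned can be said only of the current Appendix A.

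**Conclusion.** The point holds as a reporting and interpretation defect. As written, the DLT percentage is understated by up to 3.5-fold, and participants who were not assessed appear as having no DLTs.

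A uniform 3.5-fold dilution is a tempting reading, but the documents do not support it. That figure applies to Group B at its planned 35, or to Group A if pooled with Part 1 300 mg. Group C had 24 participants shortly before it was closed, which gives 2.4, and it would reach 3.5 only had it filled to 35. Part 1 200 mg is essentially unaffected.

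The conclusion rests on two assumptions. The first is that the general population rule in SAP 9.1 applies to the DLT line, since no exception is written. The second is that DLTs are recorded only among those SAP 9.2.2 says were evaluated. The Protocol's DLT definition is not itself confined to the run-in, and Protocol 4.1.2 has high-grade events in the expansion adjudicated as potentially dose-limiting. A DLT recorded outside the run-in would therefore change the factors, and a zero outside it is not strictly certain. Ascertainment would still be unequal between groups.

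**What to change.** In SAP 9.2.3 and Appendix A, report DLTs through Day 28 with the participants assessed for DLTs as denominator: Part 1 by dose, and the safety run-in participants of Groups B and C. Either a separate table or a row-specific denominator in Table 3.2.1 would do. State whether the Protocol's 21-of-28-dose rule applies to that denominator. Show Group D and newly randomized Group A participants as not evaluated instead of 0%.

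The cost is one small table or a footnote, with no new data. The reported DLT percentages will be higher and, resting on about 10 participants each, less precise. A descriptive comparison of Grade 3 or higher TEAEs in the first 28 days across Groups A, B and D would give a like-for-like view of early toxicity, but it is optional and not needed for the correction.
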